## 9.1 Primary Efficacy Analysis

The primary outcome measure was analysed in the same manner as described above and presented as the between treatment group difference in change in urine volume between the baseline and final visits.

## 9.2 Secondary Efficacy Analyses

All secondary outcomes were analysed in the same manner as the primary outcomes. Results were presented as:

- between treatment group difference in urinary sodium excretion, from the 24 hour urinary collection
- between treatment group difference in estimated glomerular filtration rate (safety endpoint)
- between treatment group difference in serum creatinine (safety endpoint)
- between treatment group difference on protein/creatinine ratio
- between treatment group difference on albumin/creatinine ratio

- between treatment group difference on the renal biomarker, cystatin C.

In analysing the results from the Renal Physiology test days, these will be analysed via a 2 way repeated measures ANOVA for both urinary volume and urinary sodium.

## **10 Safety Analyses**

An all patient group analysis was performed for safety variables (glomerular filtration rate and serum creatinine).

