We contend that these effects, albeit modest, of SGLT2 inhibitors may potentially augment the diuretic effect of loop diuretics. It is noteworthy that osmotic diuretics such as mannitol have been used alone or in combination with loop diuretics such as furosemide to promote diuresis in participants undergoing intra-cranial surgery²⁸ and in the postoperative period to prevent acute kidney injury.²⁹ In CHF, mannitol was reported to promote effective diuresis in a single centre trial in the US.³⁰ Importantly, in all these settings, mannitol, which is a potent osmotic diuretic when used in combination with furosemide, was shown to be safe and did not result in renal failure or electrolyte disturbances.

It is known that increased sodium delivery to the macula densa following SGLT2 inhibition may intensify TG feedback and lead to a decline in glomerular filtration rate at least in T2D individuals.^{25, 26} A meta-analysis on the effect of dapagliflozin on renal function that included 12 placebo controlled randomized studies and involved more than 4000 participants with preserved renal function showed that dapagliflozin caused a fall in estimated glomerular filtration rate (eGFR) at week 1 that slowly returned to baseline.³¹ This pattern of acute eGFR decline followed by stabilization suggests that the acute eGFR decline reflects a (reversible) haemodynamic change rather than worsening of structural renal function.

The renal effects of SGLT2 inhibitors in combination with furosemide in T2D with CHF are not known. The recent EMPA-REG trial demonstrated a beneficial effect of the SGLT2 inhibitor empagliflozin on cardiovascular outcomes, particularly heart failure hospitalisation in T2D.¹⁵ It is thought that the most likely explanation for this positive result is the improvement in loading conditions caused by the osmotic diuresis.³³ Therefore, there is an urgent need for a trial to provide detailed acute and long-term information regarding the renal effects of the SGLT2 inhibition in combination with furosemide, in T2D participants with stable CHF.

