5.5.2 Treatment Allocation

Participants will be given blinded medication. At the randomisation visit they will be dosed with either empagliflozin 25mg (6 weeks) or matched placebo (6 weeks) to continue once daily, with a 2-week washout period between each arm. Participants and their bloods (including U&Es and LFTs, FBC) will be monitored as per trial schedule and medication stopped if concerns arise. If trial drug needs to be stopped

due to intolerance or adverse events, they will remain in the trial in order to do an "intention to treat" analysis. They will be invited to attend all future trial visits.

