## **7.2 Analysis Populations**

The full analysis population was an intention to treat analysis, including all subjects who were randomised and received any study drug after consent.

The safety population was all subjects who received any study treatment (including control) but excluding subjects who drop out prior to receiving any treatment.

Prior to breaking the blind, each subject's inclusion or exclusion status with regard to each analysis population was established. The exact process for assigning the statuses was defined and documented prior to breaking the blind along with any predefined reasons for eliminating a subject from a particular population.

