### **9 Efficacy Analyses**

Efficacy analysis was performed on the intention to treat population as defined in section 7.2.

Data for continuous outcome measures were assessed for normality prior to analysis. Transformation of the outcome variables was used where necessary where these were not normally distributed. Outcome measures were assessed by 2 way Analysis of Variance (ANOVA). Initial comparison was between treatment groups (empagliflozin

vs placebo) at the final visit of each treatment arms (visit 5 and visit 9) adjusted for baseline measures (visit 2 and visit 6) of the outcomes.

Where data was not normally distributed and could not be transformed into a normal distribution, data were analysed using non–parametric methods. Data for categorical outcomes measures were assessed by logistic regression in the same way as described for continuous outcome measures.

All efficacy variables were listed by subject within study centre. Data were summarised by treatment group. Number, Mean, Standard Deviation, Minimum and Maximum will summarise continuous efficacy variables, whereas number and percent will summarise categorical efficacy variables.

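### The only formal comparison of eGFR and creatinine is by intention to treat at period end, so off-drug values after early stopping can dilute a renal effect of empagliflozin.

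*SAP*

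**What the plan says.** SAP 4.2 lists glomerular filtration rate and creatinine as secondary outcomes and marks both as safety endpoints. SAP 9.2 then states: "All secondary outcomes were analysed in the same manner as the primary outcomes". SAP 9 supplies the method. On population: "Efficacy analysis was performed on the intention to treat population as defined in section 7.2". On timing, empagliflozin is compared with placebo "at the final visit of each treatment arms (visit 5 and visit 9", adjusted for visits 2 and 6.

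Neither population in SAP 7.2 restricts data to time on drug. The first reads: "The full analysis population was an intention to treat analysis, including all subjects who were randomised and received any study drug after consent". The second reads: "The safety population was all subjects who received any study treatment (including control". SAP 10 opens with: "An all patient group analysis was performed for safety variables (glomerular filtration rate and serum creatinine".

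Protocol 5.5.2 says of participants whose drug is stopped for intolerance or adverse events that "they will remain in the trial in order to do an" intention-to-treat analysis, and it invites them to all later visits. The discontinuation reasons in protocol 6.8 include suspected volume depletion with vomiting and diarrhoea, symptomatic postural hypotension, and a sustained eGFR below 45 ml/min despite a change in loop diuretic dose. On the class effect, protocol 1.2 says that "the acute eGFR decline reflects a (reversible) haemodynamic change rather than worsening of structural renal function".

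**The concern.** Intention to treat answers a treatment-policy question: what happens to renal function in people assigned to empagliflozin, including those later taken off it. For a safety endpoint one also wants to know what happens while the drug is being taken. The two answers differ when stopping is related to the endpoint. Some of the protocol 6.8 reasons concern volume status, and one is defined on eGFR itself. A participant stopped for such a reason and sampled off drug at visit 5 or 9 still counts under empagliflozin. If eGFR has risen again by then, the estimated difference moves towards no effect.

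Renal safety of adding empagliflozin to a loop diuretic is a stated secondary objective, and protocol 12.4 provides for no data monitoring committee. The reported eGFR and creatinine differences will therefore carry much of the renal safety conclusion.

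**Working it through.** **The plan's own figure.** The plan gives no expected renal effect, renal SD or stopping rate, so there is no renal figure to reproduce. The denominator used below does reproduce: 22 / (1 − 0.35) = 33.8, rounded up to 34 (protocol 9.1.1, SAP 6).

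**When renal samples are taken.** Appendix 1 and SAP Table 1 schedule on-treatment safety bloods only at visits 3 and 5 in period 1 and visits 7 and 9 in period 2. Visits 4 and 8 are telephone contacts. This has two consequences:
- A fall first seen at visit 5 or 9 is itself the analysed value, because drug ends at that visit (protocol 3.1). Nothing is lost.
- A fall that leads to stopping between day 3 and period end shows only in unscheduled bloods, which no planned analysis uses. The analysed value is then off drug.

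**Dilution.** Notation:
- q = share stopped before the period-end visit and sampled there off drug
- k = stoppers' on-drug fall relative to the others' fall
- r = fraction of that fall recovered by visit 5 or 9
- a = mean fall in those who stay on drug

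On-drug mean fall = a[(1 − q) + qk]. Fall seen at period end = a[(1 − q) + qk(1 − r)]. Share lost = qkr / [(1 − q) + qk].

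The documents give none of q, k or r. The assumed ranges are k = 1 to 3 and r = 0.5 to 1, with the placebo-period mean taken as unaffected.

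| Stopped | Low (k = 1, r = 0.5) | High (k = 3, r = 1) |
|---|---|---|
| 1 of 34 | 0.5/34 = 1.5% | 3/(33 + 3) = 8.3% |
| 3 of 34 | 1.5/34 = 4.4% | 9/(31 + 9) = 22.5% |
| 20% | 0.10/1 = 10.0% | 0.60/1.40 = 42.9% |
| 35% | 0.175/1 = 17.5% | 1.05/1.70 = 61.8% |

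The last row is an extreme bound. It treats the whole planned dropout as stopping for harm, whereas the protocol attributes that dropout to the burden of the renal tests. With q = 0 or r = 0 the loss is zero.

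**In ml/min.** Assume a fall of 5 in those who stay on drug and 15 in three stoppers of 34:
- On-drug mean: (31 × 5 + 3 × 15)/34 = 200/34 = 5.88
- Period-end mean, full recovery: 155/34 = 4.56
- Period-end mean, half recovery: (155 + 22.5)/34 = 5.22

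**The case against.** Four objections have weight.

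**The eGFR stopping rule is narrow.** It needs a sustained value below 45 ml/min despite a diuretic change. With scheduled bloods only at day 3 and period end, it could be met in between only on unscheduled samples. This stands. It leaves symptom-led stops and the general provision in protocol 5.5.2 to stop drug when monitoring raises concerns, neither with a stated frequency.

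**Off-drug recovery is not documented.** A reader might take protocol 1.2 to show that stopped participants will have recovered by visit 5 or 9. It does not. It describes dapagliflozin in people with preserved renal function, with a fall at week 1 that slowly returned to baseline. It gives no recovery time after stopping. Recovery here is plausible but inferred.

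**The SAP reports more than one all-patient analysis.** SAP 10.4 summarises laboratory change at each visit, including the day-3 visits. SAP 10.1 and 10.2 report adverse events and serious events, and SAP 8.1 reports dropouts by reason. SAP 8.5 adds an adherence sensitivity analysis where non-compliance is evident, and protocol 9.3 plans a secondary analysis adjusting for changes in trial medication. These are real but partial safeguards. The laboratory summaries are descriptive, and event counts do not restore an eGFR difference. Adherence is a post-randomisation covariate that harm can affect. The protocol 9.3 analysis is not repeated in the SAP.

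**Not every stopper supplies a late off-drug value.** Those who leave the trial are offered an early discontinuation visit (protocol 5.5.4), and the SAP does not say how its values are used. If period-end values are missing, multiple imputation under missing at random (SAP 7.4) may instead pull them towards those who tolerated the drug.

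**Conclusion.** The gap is real and the direction of the risk is clear, but its size cannot be fixed from the documents. The only formal between-treatment comparison of eGFR and creatinine includes off-drug values after stopping for harm, and no on-treatment comparison stands beside it. If stoppers recover, a renal effect is understated: by about 1.5 to 8% of the mean fall for one stopper in 34 and about 4 to 23% for three, under the assumed ranges above. The loss becomes large only if many stop and recover.

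A reader might go further and infer that the trial will understate renal harm, or will find the combination safe because harmed participants were stopped in time. The documents do not support that. They give no stopping rate and no off-drug recovery rate, and they do provide by-visit and adverse event reporting. Nor is intention to treat wrong here. It is a legitimate treatment-policy analysis that should not stand alone for renal safety.

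**What to change.** Keep the planned analysis. Add to SAP 10 a supplementary on-treatment analysis of eGFR and serum creatinine:

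- For each participant and period, take the last value drawn on that period's drug, or the sample that prompted stopping, as change from that period's baseline (visit 2 or 6). Define the on-drug window so that test-day samples qualify, because the morning dose is held until partway through the test (protocol 3.2.3).
- Report the within-participant empagliflozin minus placebo difference with a 95% CI.
- Give the same comparison at the day-3 visits (3 and 7).
- List everyone who stopped early, with treatment, reason and last on-drug value.
- Report any worst-value summary that uses unscheduled samples as descriptive only, because sampling may be unequal between treatments.

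SAP 10 should also state the population, visits and attribution rule behind its all-patient analysis. If the blind has already been broken, label the addition post hoc.

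The cost is about one SAP paragraph and one or two tables from data already held; protocol 8.1 names the medical notes as the source for blood results. For a stopper with no unscheduled bloods, the last on-drug value will be the day-3 one, so the gain depends on what was sampled. No change to any stopping or dosing rule is proposed.

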### **10.1 Adverse Events**

When calculating the incidence of adverse events, or any sub-classification thereof by treatment, time period, severity, etc., each subject will only be counted once and any repetitions of adverse events was ignored; the denominator was the total population size. The adverse events will be coded using the MedDRA coding system, version 21.1 dated September 2018.

Treatment emergent adverse events are those events that occur after the baseline assessment. Those subjects with adverse events that worsen post-treatment will also be included. The incidence of AEs that are judged to be related to the treatment was reported.

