At week 9, participants will have safety and research bloods drawn, vital signs recorded, new trial medication dispensed, educated on the symptoms of hypoglycaemia and given a written action plan on how to manage it in the unlikely event that it occurs.

Participants will subsequently return to the CRC after 3 days (±2 days), for a trial day, lasting approximately 5 hours, where they will have safety and research bloods drawn again, vital signs recorded and will undergo renal physiological tests (RPT). Participants will be required to provide several urine samples throughout the course of the visit.

Participants will then return again at week 14 for the final trial day, lasting approximately 5 hours, where they will undergo RPT again, safety and research bloods will be drawn and vital signs recorded. Participants will be required to provide several urine samples throughout the course of the visit. Participants will terminate trial drug, either empagliflozin 25mg or placebo.

Further details of trial visits are detailed in section 7.1.

Participants not on insulin will continue with all usual medications, these remain unchanged throughout unless clinically indicated. Participants who are already on insulin at time of recruitment will be advised of the likelihood of having to reduce their total daily dose of insulin by for example by a reduction of 10% on the day they are randomised with an increase in the frequency of their blood sugar monitoring. Further dose titration will be done by the trial team, Diabetic Consultant, or GP with or without instruction from either the trial team or Diabetic Consultant, based on the participant's symptoms, home and laboratory-based blood sugar levels. Down-titration of therapy will be done in a stepwise manner starting with insulin. Other anti-diabetic agents will only be down-titrated once insulin has been discontinued. Up-titration of the IMP.

Acute exacerbations of CHF are likely to occur in the course of this trial. These will be treated as per usual practice and the empagliflozin or placebo will not need to be stopped unless the participant or their clinician specifically requests stopping or there are sound clinical reasons to do so. Anti-hyperglycaemic medications may be adjusted by the participants GP, hospital care consultant or PI as necessary during the trial; changes will be recorded in the concomitant medications.

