3.2.3 Renal Physiological Tests

Participants will attend the Clinical Research Centre (CRC) on 4 separate trial days (2 while in each arm of the trial). On each trial day, participants will present themselves to the CRC, following an overnight fast. Two days before presenting to the CRC, participants will be required to follow a 2gm sodium and 2L fluid/day controlled diet. A 24-hour urine collection will be made in the 24 hours prior to the day of the renal physiological test. Participants will be asked to take their morning usual medications except their IMP (empagliflozin or placebo) and furosemide (or equivalent loop diuretic).

[figure not shown]
An intravenous cannula will be placed in each arm for subsequent infusion and blood sampling. Bloods will be drawn for measurement of plasma NT-proBNP (a biomarker of wall stress and will be measured as a discovery variable in this proof of concept trial) using standard protocols. Firstly, a 15 ml/kg oral water load will be administered over approximately a 15-minute period. Thereafter, at approximately 30 minute intervals, participants will be requested to void urine until the end of the trial day. The volume of urine passed will be measured and an aliquot stored for later analysis. On each occasion, the volume of urine passed will be measured, and an equal volume of water given to drink. In this way, a steady state diuresis will be established over approximately 3 hours. The last urine collection during this stabilization period will be taken as baseline. Approximately 3 hours after initiation of the test, each participant will receive an oral tablet of either empagliflozin 25mg or placebo. After the seventh urine sample, participants will be given a bolus of IV furosemide at half their total daily dose. Heart rate will be displayed continuously on an ECG oscilloscope and the blood pressure measured approximately every 60 minutes. Venous blood will be obtained at the midpoint of each clearance period for measurement of serum sodium, osmolality and creatinine. At the end of the RPT, light refreshments in the form of tea, coffee or juice with biscuits will be provided. A lunch will then be provided at the CRC.

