## **8 Summary of Study Data**

[figure not shown]
All continuous variables were summarised using the following descriptive statistics: n (non–missing sample size), mean, standard deviation, median, maximum and minimum. The frequency and percentages (based on the non–missing sample size) of observed levels were reported for all categorical measures. In general, all data were listed, sorted by site, treatment and subject, and when appropriate by visit number within subject. All summary tables were structured with a column for each treatment in the order (Intervention, Control) and was annotated with the total population size relevant to that table/treatment, including any missing observations.

Baseline characteristics for patients are: age, gender, past medical history, BMI, smoking history, blood pressure, HbA1c, eGFR, medication classes, severity of heart failure as identified by the ejection fraction (mild, moderate or severe), and medication classes.

Concurrent illnesses and medical conditions were recorded and listed but not analysed.

Patient medication was recorded at baseline and at each study visit. Anti–diabetic, diuretic and anti–hypertensive drug classes were reported.

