### **8.1 Subject Disposition**

From the CRF it was established how many subjects reached what stage of the trial, how many dropped out and for what reasons (death, toxicity, treatment failure, withdrew consent). It was therefore identified the number screened, randomised, completed treatment 1, completed treatment 2, and ultimately how many completed the study.

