#### **8.5 Treatment Compliance**

The calculation of adherence was performed and reported as a percentage, where the number of tablets issued minus the number of drugs returned, was then divided by the number of drugs that should have been taken. This was performed by the PI at visit 3 and visit 7, and by the Pharmacy department at visit 5 and visit 9.

Adherence of 80–120% will be deemed as being compliant. Where an issue of non-compliance was evident, a sensitivity analysis was performed and adherence was included as a covariant.

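### SAP 10.1, read literally, divides by-treatment adverse event counts by everyone dosed, including participants who never took that treatment; it needs reconciling with SAP 8

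*SAP*

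**What the plan says.** SAP 10.1 opens with its scope: "When calculating the incidence of adverse events, or any sub-classification thereof by treatment, time period, severity, etc". For all of these breakdowns it then gives one counting rule and one denominator: "each subject will only be counted once and any repetitions of adverse events was ignored; the denominator was the total population size".

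SAP 7.2 defines two populations, and both are pooled. The full analysis population is everyone randomised who received any study drug. The safety population is everyone who received either treatment. No population is defined by exposure to empagliflozin or to placebo separately.

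SAP 8 sets a convention for summary tables: one column per treatment, "annotated with the total population size relevant to that table/treatment". It also bases percentages for categorical measures on the non-missing sample size, which is a different rule from 10.1.

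SAP 8.1 describes disposition: "It was therefore identified the number screened, randomised, completed treatment 1, completed treatment 2, and ultimately how many completed the study". These are counts of who completed each treatment, not of who started it.

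**The concern.** In a parallel trial, a participant belongs to one arm and the column total is obvious. In an AB/BA crossover, each participant contributes to both treatment columns, but only after taking both treatments. The second treatment is not handed out until after washout (Protocol 3.1: "At week 9, participants will have safety and research bloods drawn, vital signs recorded, new trial medication dispensed"). Someone who leaves in period 1 therefore never takes it and cannot have an adverse event on it. Keeping that person in its denominator lowers the reported rate.

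Such losses are foreseen. Protocol 4.1 and the sample size sections of both documents plan for 35% dropout and attribute it to the burden of four test days. Protocol 3.2.3 places two of those days in each arm, so part of that burden falls before crossover.

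What is at stake is the by-treatment adverse event table. Its rates could be too low for one or both treatments, and if losses differ between sequences the comparison of the two columns would shift for a reason unrelated to safety. Two analysts following the same SAP could also report different percentages.

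**Working it through.** **The plan's own figure.** SAP 6 requires 22 participants and assumes 35% dropout: 22 / (1 − 0.35) = 33.8, rounded up to 34. The stated total is reproduced. The planned loss is 34 − 22 = 12 (0.35 × 34 = 11.9). The documents give no adverse event rate or denominator to reproduce.

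**Formula.** Let N be all dosed, *a* the number lost in period 1 on empagliflozin (never took placebo), and *b* the number lost in period 1 on placebo (never took empagliflozin).

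- Reported / per-exposed incidence, empagliflozin: (N − b) / N
- Reported / per-exposed incidence, placebo: (N − a) / N
- Factor applied to the empagliflozin-to-placebo ratio: (N − b) / (N − a)

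No event rate has to be assumed.

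**Assumptions.** The documents do not say when the 12 losses occur or how they split between sequences. Losses before crossover are therefore taken from 0 to 12 of 34. Six is used as a middle case because two of the four test days precede crossover.

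| Lost on empagliflozin / placebo (a/b) | Took empagliflozin | Took placebo | Empagliflozin, reported/correct | Placebo, reported/correct | Ratio factor |
|---|---|---|---|---|---|
| 0/0 | 34 | 34 | 1.000 | 1.000 | 1.00 |
| 3/3 | 31 | 31 | 0.912 | 0.912 | 1.00 |
| 4/2 | 32 | 30 | 0.941 | 0.882 | 1.07 |
| 2/4 | 30 | 32 | 0.882 | 0.941 | 0.94 |
| 6/6 | 28 | 28 | 0.824 | 0.824 | 1.00 |
| 12/0 | 34 | 22 | 1.000 | 0.647 | 1.55 |
| 0/12 | 22 | 34 | 0.647 | 1.000 | 0.65 |

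The 3/3 row understates both treatments by 1 − 31/34 = 8.8%, and the 6/6 row by 1 − 28/34 = 17.6%. For scale, an assumed per-exposed incidence of 20% would be printed as 18.2% (× 31/34), 16.5% (× 28/34) or 12.9% (× 22/34).

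**How likely is an uneven split?** Suppose six leave before crossover, leaving is unrelated to treatment, and the sequences hold 17 each (an assumption; no allocation counts are given). The split is then hypergeometric. P(3/3) = 0.344 and P(4/2 or 2/4) = 2 × 0.2407 = 0.481. The factor therefore lies between 0.94 and 1.07 with probability 0.825.

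**Replacement.** Protocol 5.5.4 allows withdrawals to be replaced, which raises N. With six replaced by completers, N = 40. A 3/3 split then gives 37/40 = 0.925 (7.5% understatement), and 4/2 gives 38/36 = 1.06.

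**The case against.** The strongest reply is that the literal reading is not the intended one. An adverse event table is a summary table. SAP 8 annotates such tables with a population size relevant to the treatment, and 10.1 uses nearly the same phrase. The clause that opens 10.1 could also scope the population by treatment, just as it scopes the count of subjects. This stands as a plausible reading, and it is why the point is an ambiguity to reconcile and not a clear conflict. It does not settle the matter. SAP 8 governs how a column is annotated, does not say that relevant means exposed, and includes missing observations in the number. SAP 10.1 neither refers to it nor repeats the qualifier.

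A second reply is that losses will be visible. SAP 8.1 reports completion by treatment, and Protocol 5.5.4 requires a description of those lost, including how the loss relates to treatment and outcome. That makes a distortion easier to notice, but it does not define the denominator.

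A third is that dropout is not the same as never starting the second treatment. This is correct. Protocol 5.5.2 keeps participants who stop drug in the trial, and some of the 12 may leave after crossover. The 0 to 12 range is therefore an assumption, not a forecast.

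A reader might go further and infer that the trial's safety conclusions are biased, or biased towards one treatment. The documents do not support that. They give neither the timing nor the split of losses, so the direction is unknown. The named safety endpoints, eGFR and creatinine, do not use this denominator. Nor do gaps in how 10.1 handles the period 2 baseline or washout events add weight: SAP 9 already names visits 2 and 6 as baselines for the outcome analyses, and 10.1 already allows display by time period.

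**Conclusion.** The point holds as a narrow one, at low severity. SAP 10.1 states a denominator that, applied literally, gives too low a rate for any treatment that some dosed participants never took. SAP 8 may intend something better but does not say so.

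The error is zero if nobody leaves before crossover. If losses are balanced, both columns are understated equally: 8.8% with six lost and 17.6% with 12. The between-treatment ratio moves only with unequal losses: by 1.07 or 0.94 for a 4/2 split of six, and by 1.55 or 0.65 in the extreme where all 12 come from one sequence. These figures rest on N = 34 dosed, on the planned dropout as the ceiling, and on assumed timing and splits. The primary result and the eGFR and creatinine comparisons are untouched.

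**What to change.** Add to SAP 10.1 that the denominator for incidence by treatment is participants who took at least one dose of that treatment, and that overall incidence uses the safety population of SAP 7.2. Say in SAP 8 that the population size shown for a treatment column in adverse event tables is that same exposed number, so that the two sections agree.

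The cost is a sentence or two and a small change to the table program. No new data are needed. Drug is dispensed at randomisation and again at week 9, and SAP 8.5 already provides for tablet counts in both periods: "This was performed by the PI at visit 3 and visit 7, and by the Pharmacy department at visit 5 and visit 9". Those records identify who took each treatment. If the table has already been produced, check which denominator was used and, where it was all dosed, recompute the percentages from the same counts.
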